## **Summary of Primary and Secondary Analyses**

**Primary Efficacy Endpoint:** Percent of patients with  $\geq 50\%$  reduction from baseline in % Body Surface Area of disease at 12 months, using the “patients contributing data with clinical staging IA and IB and using mechlorethamine (continuing and new) plus corticosteroids + possibly another treatment” analysis population.

### **Secondary Analyses will include:**

- Percent of patients with  $\geq 50\%$  reduction from baseline in % Body Surface Area of disease at each visit preceding and following the 12 month visit
- Overall Response Rate 2 (ORR2) Percent of patients with  $\geq 50\%$  reduction from baseline in % Body Surface Area of disease for at least two consecutive visits.
- Overall Response Rate 4 (ORR4) Percent of patients with  $\geq 50\%$  reduction from baseline in % Body Surface Area of disease for at least four consecutive visits. Further description of the ORR4 endpoint is shown in [Prince et al 2017].
- Time to Next Treatment (TTNT). Further description of the TTNT endpoint is shown in [Hughes and Prince 2014].
- Rates of on-study hospitalization

- Change from baseline in PRO questionnaires:
  - a. Pruritis VAS
  - b. SkinDex-29
  - c. MF/SS CTCL QOL instrument

## METHODS FOR HANDLING MISSING DATA

Because this is an observational study, data that are not present at a particular assessment will generally reflect clinical practice rather than a data quality issue. As data are not expected to be missing at random, no plan exists to impute missing data or utilize models which

assume data are missing at random. For any results considered for external dissemination (e.g. publication), additional analyses will need to be conducted to compare the patients who did and did not contribute data to the analysis to assess the potential for bias.

Type of Date	Date is incomplete	Date is completely missing
Date of Valchlor start or discontinuation	Valchlor start: If the month and year is present but the date is missing then impute the 15th day of that month. Valchlor discontinuation: If day of Valchlor discontinuation is missing and month and year are present, day is replaced by the 15 th .	Valchlor start: No replacement Valchlor discontinuation: If observation period under Valchlor is stopped due to adverse event or loss to follow-up, but no Valchlor discontinuation date is provided, the Valchlor discontinuation date is respectively the date of adverse event reported on the Termination CRF or last treatment information date available (for lost to follow-up) or withdrew consent or physician decision to withdraw.
Date of start event leading to reason for Valchlor prescription	If year is known then impute 30 th June of that year. If year and month is known then impute 15 th of that month and year. If imputed day (using rules above) is after date of enrollment, then impute enrollment date – 1 day.	No replacement
Date of medication start/stop date	If year is known then impute 30 th June of that year. If year and month is known then impute 15 th of that month and year. If imputed day (using rules above) is before start date of Valchlor, then impute start date of Valchlor + 1 day. Year & month present, day missing: If month and year is the same as data cut then use the data cut. If month and year is before the data cut then use 15 th of that month. Year present, Month missing: If year is the same as the data cut the use the data cut. If the year is before the data cut then use 30 th of June of that year.	No replacement

Statistical Analysis Plan  
Valchlor PROVe  
November 2019  
Version Number: 3.0

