5.6 Data management

5.6.1 Data collection

Informed consent must be obtained prior to enrollment and data collection.

Re-consent must be obtained for patients that were enrolled in the study prior to Amendment 1 and still ongoing to complete 24 months of data collection from the enrollment date. Instead of the 12 months initially planned.

This study will collect data on MF-CTCL patients being treated with Valchlor [see Section 5.2.1 for inclusion criteria] under routine clinical care. This will include both data collected from assessments that are routinely performed for MF-CTCL patients being treated with Valchlor in clinical practice, and additional data from further assessments that may be performed.

No specific clinically mandated assessments are to be performed as part of study participation. Patient-completed questionnaires, however, are a study requirement and will be collected at all clinic visits during the study observation period. These questionnaires will be administered on paper by study coordinators. Patient clinical data (non-patient-completed) will be collected from the patient's medical records at enrollment and throughout the study period. All data will be entered into an eCRF at the time of collection or on a quarterly basis by study coordinators. AEs, reports of secondary exposure, and SAEs whether or not related to Valchlor will be entered into the eCRF at every visit and upon notification by the patient (e.g., reported via phone call).

A secure, Internet-based electronic data collection (EDC) system will be used for data entry and hosting. An audit trail will be maintained by the EDC system for all data entries and changes, indicating what entries/changes have been made, who made them, and when. Data will be encrypted when transferred over the Internet and will be stored in a secure database protected from unauthorized access.

All data collected will be de-identified before transmission to the central study coordinating center. Patient names will not be collected. Other patient identifiers will be collected in order to allow identification of study patients when SAEs are received by US Drug Safety outside of the study [see Section 7.4].

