5.7 Data analysis

5.7.1 Analysis sets and groups

Demographics and clinical characteristics will be summarized for all enrolled patients and also grouped separately for patients continuing treatment with Valchlor versus patients who are newly initiating Valchlor. Use of prior treatments and past methods of assessing response will be similarly analyzed separately for the two groups. The methods used for assessment of response (i.e., assessed with that method versus not assessed with that method, either at follow-up alone or in tandem with a prior assessment) will be reported as cumulative percentages over time and also as a percentage of first visits, second visits, etc. To minimize the potential impact of missing data, analyses will focus on variables that are available for all patients, such as whether a particular type of assessment occurred, rather than focusing on the results of a particular assessment. Analyses of response, based on a particular measure of response, will be limited to patients for whom that measure was reported. Therefore, patients with reported data will be compared to patients without any reported data with respect to demographics and pre-treatment clinical status to identify potential biases. The summary of response rates will be tabulated and the definition of response will be detailed in the Statistical Analysis Plan.

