## ANALYSIS POPULATIONS

This study will enroll approximately 300 MF-CTCL patients who are being treated (newly initiated or continuing treatment) with Valchlor from up to 50 participating university-affiliated hospitals, community hospitals, or community clinics in the United States.

Patients considered 'being treated with Valchlor' are composed of two distinct groups:

- 1) Patients who are newly initiating Valchlor treatment (i.e. patients who have initiated Valchlor within 30 days or fewer prior to enrollment) and,
- 2) Patients who are continuing treatment with Valchlor (i.e. patients who have been on Valchlor for more than 30 days prior to enrollment).

Patients in either group must be treated with Valchlor at enrollment to be eligible for the study.

All consecutive MF-CTCL patients who are receiving Valchlor at participating US centers are eligible for enrollment in the study, regardless of other MF-CTCL therapies received before or at the time of enrollment.

The primary efficacy endpoint will be the proportion of subjects who are responders to treatment at the 12-month timepoint using a  $\geq 50\%$  reduction from baseline in BSA as the definition of a responder in the group of patients who used mechlorethamine plus corticosteroids and possibly another treatment. Since PROVe did not require a specific visit schedule, the primary 12-month analysis will include patients with a post-baseline % BSA score that falls within a window of  $365 \pm 90$  days. Please note that in this observational trial, patients continued on study even if they permanently discontinued mechlorethamine gel for any reason and switched to new therapy. Given this, such patients (15-20%) will be excluded from the analysis at 12 months. A sensitivity analysis will be conducted for the primary analysis using the full dataset. We will compare this to the subset of patients who discontinued mechlorethamine gel (Table 21a).

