## **Missing versus No Assessment**

For patients who do not have any assessments reported on the eCRF for a completed visit, the negative response for the assessment is required and collected to document the absence of the assessment. In addition, for patients that do not have at least 1 clinic visit during a quarter, an affirmative response that the patient is still under care by the site will be requested quarterly. Thus, missing data is not anticipated due to the eCRF requirements for responses and the absence of reported assessments can be interpreted the same as the absence of actual assessments.

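### The primary 12-month BSA response rate covers only patients with BSA in the window, while the SAP leaves the protocol's check on everyone else conditional, unspecified and without a table

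*SAP*

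**What the plan says.** **How BSA arises.** Protocol 5.6.1 states: "No specific clinically mandated assessments are to be performed as part of study participation". Visits are unscheduled (Protocol 5.1), and pre-treatment data are recorded as available (footnote to Protocol Table 1). The SAP's Assessment Schedule warns that an enrollment BSA may not be a true baseline if Valchlor was already in use.

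**Who is counted.** In SAP Analysis Populations, "the primary 12-month analysis will include patients with a post-baseline % BSA score that falls within a window of" 365 ± 90 days, that is, days 275 to 455. The Summary of Primary and Secondary Analyses takes as headline the stage IA/IB patients using mechlorethamine plus corticosteroids, with or without another treatment.

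**What the protocol promised alongside.** Section 5.7.1 accepts the restriction: "Analyses of response, based on a particular measure of response, will be limited to patients for whom that measure was reported". It then adds, without condition, that "patients with reported data will be compared to patients without any reported data" on demographics and pre-treatment clinical status, to look for bias. The synopsis repeats this. Section 5.8 promises that the extent of missing data and its effect on the estimates will be assessed.

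**What the SAP does.** Under Methods for Handling Missing Data: "As data are not expected to be missing at random, no plan exists to impute missing data or utilize models which" rest on a missing-at-random assumption. The comparison follows: "For any results considered for external dissemination (e.g. publication), additional analyses will need to be conducted to compare the patients who did" or did not contribute to the analysis. No variables or method are given. Analysis Populations separately argues that, since no intended treatment was prevented, the planned analyses carry no possibility of selection bias.

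**The concern.** A patient who dies, withdraws, is lost, is not seen between days 275 and 455, is seen without a BSA, or has no valid baseline BSA drops out of the denominator. To read the contributors' percentage as the rate for the treated population, one must assume that non-contributors respond at the same rate. A missing-at-random method needs that only among patients alike on observed characteristics. The SAP therefore rejects such methods because their assumption is doubtful, then reports a figure that needs a stronger one.

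The protocol's safeguard was the comparison of contributors with non-contributors. Under the SAP its content can be settled after the response rate is known, and an internal report could omit it. If patients doing well, or patients doing badly, are measured less often, the headline rate is biased in a direction the prespecified tables would not reveal.

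**Working it through.** **1. The passages side by side**

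| Item | Protocol | SAP |
|---|---|---|
| Response limited to patients with the measure | Yes (5.7.1, synopsis) | Yes (Analysis Populations) |
| Comparison with patients lacking it | Unconditional | Only for results considered for dissemination |
| Comparison variables | Demographics, pre-treatment clinical status | None named |
| Impact of missing data on estimates | To be assessed (5.8) | No analysis for absent BSA |
| View of missingness | Potential bias to be examined | Not at random in one section; selection bias ruled out in another |

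The last two SAP statements cannot both stand. The argument for no selection bias concerns whether treatment was given as intended, not whether a BSA was recorded.

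**2. Search of the planned outputs.** None of Tables 1 to 28 or Listings 1 to 9 compares contributors with non-contributors. Table 7 counts assessment methods. Table 21a, the one sensitivity analysis of the primary endpoint, uses the full dataset and concerns patients who discontinued mechlorethamine; nothing says it assigns a value to a patient without BSA in the window.

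**3. The plan's own figures.** The only precision figures are in Protocol 5.5. With p = 0.5 and 95% confidence (neither is stated; both are assumed), the margin is 1.96 × √(0.25/n):
- n = 270: 5.96 points (stated 6)
- n = 200: 6.93 points (stated 7)
- n = 100: 9.80 points (stated 10)
- Enrollment: 270 / 0.90 = 300 (stated 300)

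These reproduce. They concern clinical status and hospitalization with up to 10% non-evaluable. No expected share of patients with BSA is given, so the next step is illustrative.

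**4. Bounds.** Let N be the eligible population, n the contributors and r the responders among them.
- Missing = non-responder: r / N
- Missing = responder: (r + N − n) / N
- Width: (N − n) / N, the non-contributing share

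Inputs: 88 topical corticosteroid users during mechlorethamine, all stages (SAP Table 28). The SAP excludes 15–20% as patients who discontinued and switched. Assuming that share applies to these users, 88 × 0.85 = 74.8 and 88 × 0.80 = 70.4, so N is about 70 to 75. Also assumed: n = 50 and r = 30, an observed rate of 60%.
- N = 75: 30/75 = 40.0%; (30 + 25)/75 = 73.3%; width 33.3 points
- N = 70: 30/70 = 42.9%; (30 + 20)/70 = 71.4%; width 28.6 points

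Varying the contribution at N = 75 with an observed rate of 50%:

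| Share contributing | n | r | Bounds |
|---|---|---|---|
| 90% | 68 | 34 | 45.3% to 54.7% |
| 70% | 52 | 26 | 34.7% to 65.3% |
| 50% | 38 | 19 | 25.3% to 74.7% |
| 30% | 22 | 11 | 14.7% to 85.3% |

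At the SAP's minimum of 20 patients for an analysis, 10 responders give 10/75 = 13.3% to 65/75 = 86.7%.

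**The case against.** The strongest defence is that the SAP follows the protocol. Restricting response to patients with the measure is the protocol's own rule, and the SAP labels its columns as patients contributing data. A reader might infer that the contributors-only rate is itself a departure; it is not.

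Nor has the comparison been dropped. It is required for anything disseminated, and Protocol section 8 plans publication, so the condition would probably be met. The SAP wording is in one respect broader: it applies analysis by analysis, where the protocol speaks of patients with no reported data at all. What remains is that the comparison is conditional, its content is open, and it has no place in the outputs.

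A reader might also infer that attrition would be invisible. That goes too far. Tables 6a to 6c and 7 show how often BSA was assessed, Tables 1A and 1B cover time on study and early termination, and Listings 6 and 8 give disposition and BSA by visit. What is missing is their assembly by population, stage and window beside Table 21.

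The SAP sentence that "missing data is not anticipated due to the eCRF requirements for responses" might be read as a claim that every patient will have BSA. In context it distinguishes a blank field from an assessment not done, and the Assessment Schedule accepts that not all data may be available. No criticism rests on it.

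Finally, the protocol never promised bounds, and it calls the response summary descriptive rather than an estimate of efficacy (5.7.4). The absence of bounds is thus a gap, not a contradiction. But the SAP now names a primary efficacy endpoint, which makes some sensitivity analysis for absent BSA reasonable.

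**Conclusion.** The point holds. The SAP declares its data not missing at random, reports a complete-case headline rate, and leaves the protocol's companion comparison conditional, without variables and without a shell. No sensitivity analysis covers patients without BSA in the window, and the statement that selection bias is impossible is wrong.

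The size cannot be established from the documents. The firm result is that the bounds are as wide as the non-contributing share. The ranges of 40% to 73% and 43% to 71% rest on assumed counts (30 of 50), on applying the 15–20% exclusion to corticosteroid users, and on an all-stage figure; the IA/IB set is probably smaller. It would be tempting to use all 88 as the denominator, but that counts excluded switchers as missing BSA and overstates the width. Nothing here shows that the rate is biased, or in which direction. This should be fixed as a cheap improvement; it does not invalidate the analysis.

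**What to change.** - In SAP Methods for Handling Missing Data, remove the dissemination condition so that the comparison is always done.
- Add one shell comparing contributors with non-contributors to the primary BSA analysis on demographics, stage, pre-Valchlor BSA and clinical status, and last clinician-assessed status.
- Beside Table 21, by population and stage column, show N in the population, N excluded as switchers, N with baseline BSA, N with BSA in the window, and N dead, withdrawn or lost before day 275. Table 1B has no row for death, so that count needs its own source.
- Add two sensitivity rows to Table 21: missing = non-responder and missing = responder.
- Delete the selection-bias sentence in Analysis Populations.

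The cost is some SAP wording, one shell, a block of counts and two rows. No new data are needed. The downside for the sponsor is a visibly wider range beside the headline rate.

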5.2.1 Inclusion criteria

- All adult patients (≥ 18 years of age) diagnosed with MF-CTCL and being treated with Valchlor. This includes patients newly initiating Valchlor OR patients continuing treatment with Valchlor:
 - Patients newly initiating Valchlor are patients who have their first office visit after having initiated Valchlor.
 - Patients continuing treatment with Valchlor includes patients who are actively taking Valchlor on the day of enrollment.
- Signed patient informed consent.

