## ASSESSMENT SCHEDULE

Demographics, medical history, current and historical MF-CTCL treatments, clinical status by physician, clinical status assessments, the Visual Analogue Scale (VAS) for pruritus, the Skindex-29, and ongoing adverse events (AEs) and serious adverse events (SAEs) related to Valchlor are collected at the enrollment visit, per routine clinic visits. Any data that is not collected at enrollment or present in the historical patient information will be indicated as not assessed, not applicable or not done, as appropriate. In addition, to appropriately construct change from baseline analyses all baseline data must be verified as such. For example, if a % BSA score is provided at enrollment, it may not represent a baseline disease score if a subject was already using mechlorethamine prior to the collection of that score. The same handling should apply to the PRO questionnaires.

Change in TNMB classification, change in medical history, change in medications with Valchlor and other MF-CTCL treatments, HCU, clinical status by physician, clinical status assessments, VAS for pruritus, the Skindex-29, reports of secondary exposure, and all AEs and SAEs related and unrelated during Valchlor use and >30 days after Valchlor discontinued are collected at follow-up visits during the observation period, as recorded during the routine clinic visit. These visits occur at the physician's discretion (i.e., they are not scheduled per protocol); consequently, the number of follow-up visits will vary across patients. Additionally, the data collected during the visits will be dependent upon routine clinic practice, and thus not all data may be available.

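### Partial Valchlor dates are set to the 15th without logical bounds, so an imputed start can fall after enrollment or an imputed stop before its own start (minor)

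*SAP*

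**What the plan says.** The table in the SAP section on missing data has three rows of date rules.

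- **Valchlor's own dates.** For a start, "Valchlor start: If the month and year is present but the date is missing then impute the 15th day of that month". For a stop, "If day of Valchlor discontinuation is missing and month and year are present, day is replaced by the 15"th. No limit follows either rule.
- **Event leading to the prescription.** Here there is a limit: "If imputed day (using rules above) is after date of enrollment, then impute enrollment date" minus 1 day.
- **Medication start and stop dates.** Again there is a limit, tied to the Valchlor start: "If imputed day (using rules above) is before start date of Valchlor, then impute start date of Valchlor + 1 day". A data-cut rule is added.

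On eligibility, the SAP (Analysis Populations) says "Patients in either group must be treated with Valchlor at enrollment to be eligible for the study". Protocol 5.2.1 agrees: "Patients newly initiating Valchlor are patients who have their first office visit after having initiated Valchlor".

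On baselines, the SAP (Assessment Schedule) requires them to be verified. It warns that for a BSA score given at enrollment "it may not represent a baseline disease score if a subject was already using mechlorethamine prior to the collection of that score", and it applies the same caution to the patient questionnaires. It gives no procedure for the verification.

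**The concern.** A start after enrollment contradicts eligibility, and a stop before its start is impossible. The rule can produce both. The rows below it show that the authors saw the need for limits on imputed dates but did not put them on the study drug itself.

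Valchlor dates feed several results: exposure days, tubes per month (tubes divided by time between start and stop) and the placing of other therapies relative to enrollment. They may also feed the decision on whether a score is a true baseline. That last use matters most. The baseline is the reference for the primary endpoint (a BSA reduction of at least 50% at 12 months), the by-time analyses, ORR2, ORR4 and the questionnaire changes.

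**Working it through.** The plan gives no figure for this rule, so there is none to reproduce.

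**When the rule misplaces a start.** The imputed start falls after enrollment exactly when start and enrollment share a month and enrollment is on day 14 or earlier. The true gap is then at most 13 days (start on the 1st, enrollment on the 14th).

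**Examples.**
- Enrollment 6 June, start recorded only as June: imputed start 15 June, 9 days after enrollment.
- Start 20 March, stop recorded only as March: imputed stop 15 March, and 15 − 20 = −5 days.
- End of observation 5 March, stop recorded only as March: imputed stop 15 March, 10 days after observation ended.
- Knock-on from the first example: a steroid recorded as starting in May is imputed to 15 May. That is before 15 June, so the medication row moves it to 16 June. Under the SAP's rule for other MF-CTCL treatments the patient is then not on that steroid at enrollment. With a true Valchlor start of, say, 3 June, the steroid would have been dated 4 June and counted.

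**How often, given that the start day is missing.** Take every enrollment day from 1 October 2014 to 30 September 2017 (the quarters in Protocol section 2; 1,096 days, 36 months) and true gaps of 1 to 30 days (the SAP's definition of a new patient). All combinations are assumed equally likely.
- Cases: 1,096 × 30 = 32,880.
- Misplaced starts per month: for enrollment day e from 2 to 14 there are e − 1 possible starts, and 1 + 2 + … + 13 = 91. Over 36 months: 91 × 36 = 3,276.
- Share: 3,276 / 32,880 = 10.0%.
- By gap: 1 to 7 days, 70 × 36 / (1,096 × 7) = 32.8%; 8 to 14 days, 21 × 36 / (1,096 × 7) = 9.9%; 15 to 30 days, 0%.
- With the next row's limit (enrollment minus 1 day): 0%.

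**Number of patients.** Expected number = 300 × share new × share with missing start day × 0.0996. The enrollment of 300 is from Protocol 5.5, which also names new initiators as an example of a subgroup of a third or more. The upper value of one half and the 2% to 20% missing are assumptions.
- Low: 300 × 1/3 × 0.02 × 0.0996 = 0.2.
- High: 300 × 1/2 × 0.20 × 0.0996 = 3.0.
- Primary set: SAP Table 28 shows topical corticosteroids during treatment in 88 of 289 (30%). If misplaced starts are spread in proportion, 0.2 × 88/289 = 0.06 and 3.0 × 88/289 = 0.9, before the staging and 12-month BSA filters.

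**Stop before start.** Take a 30-day month with start and stop both in it, only the stop day missing, and all ordered days equally likely. The error needs a start on day 16 or later.
- Restart interval: 120 / 465 = 25.8%.
- First interval, which must also span enrollment: C(17,3) / C(32,3) = 680 / 4,960 = 13.7%.

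**The case against.** The strongest reply concerns the baseline. Because every patient is on Valchlor at enrollment, the natural reading is that an enrollment BSA is an on-drug value. The documents keep the two apart by source: pre-treatment BSA is a separate item (Protocol synopsis, Data Sources; Table 1 footnote), and SAP Table 6a covers the time before Valchlor while Table 6b covers the enrollment visit. The SAP's test is whether the patient was already using the drug, not which date is earlier. This stands in large part. A reader might infer that on-drug scores do enter the primary endpoint as baselines; the documents do not establish that. Nor do they exclude it. No verification procedure is given, pre-treatment data are collected only as available, and the entry-time edit checks in Protocol 5.8 cannot see a date created at analysis.

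Two further inferences fail.

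- **New versus continuing.** A reader might think the missing bound distorts this split. It does not. A start imputed after enrollment needs a true gap of at most 13 days, so the patient is new and stays new. Crossings of the 30-day line come from the 15th itself when the months differ: start 20 March and enrollment 16 April is a true gap of 27 days and an imputed gap of 32. A cap at enrollment never acts there.
- **Early tolerability.** Adverse events are summarized as numbers and percentages of patients (SAP Statistical Methods, Table 18), with no exposure-day denominator.

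The end-of-study case is also partly covered. The SAP defines on-study exposure within the observation period, so mainly total exposure time is left open.

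**Conclusion.** The gap is real but minor. The rule, as written, can yield impossible dates, and the limits it lacks are already used elsewhere in the same table. Negative exposure and shifted other-therapy dates follow directly from it. A mislabelled baseline follows only if verification is done by date comparison, and its direction of bias cannot be read from the documents.

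The expected size is about 0.2 to 3 of 300 patients with a start after enrollment, and about 0.06 to 0.9 in the corticosteroid set. This rests on the assumed missingness, the assumed share of new patients and uniform dates. A reader who looks only at same-month start and enrollment would get a much larger share, 105/465 = 22.6% with ordered day pairs equally likely or 14/30 = 46.7% with enrollment day uniform. Those figures are conditional on an uncommon situation and do not describe the study. On its own the point does not threaten the primary result. In small groups one patient can still show: the SAP analyzes groups from N = 20 and summarizes those of 10 to 19, where one patient is 5 points at 20 and 10 points at 10.

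**What to change.** Add bounds to the Valchlor row.

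- **Imputed first start:** the 15th, but no later than the enrollment date (or the enrollment date minus 1 day, as in the next row), and no later than any recorded stop of that interval.
- **Imputed stop:** the 15th, but no earlier than the start of its own interval and no later than end of observation. For the interval ongoing at enrollment, also no earlier than enrollment.
- **Baseline:** do not accept an enrollment BSA or questionnaire score as pre-Valchlor on an imputed start date alone. Use the recorded pre-treatment value, or treat baseline as missing.

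The choice of cap has a small consequence. With minus 1 day, the steroid in the June example moves to 6 June and still counts as ongoing at enrollment; with a cap at enrollment it moves to 7 June and does not. Against that, minus 1 day leaves the recorded month when enrollment is on the 1st. Either is workable if stated.

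The cost is a few words in the table and a few lines of code. The downside is that a few patients may lose a usable baseline. Reporting how many Valchlor dates were imputed, and how many met a bound, would settle the size of the issue.
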